5.1.3.2 Criteria for Resuming Treatment

Subjects may resume treatment with nivolumab and ipilimumab (weeks 1-24) or nivolumab (weeks 2-52) when drug-related AE(s) resolve(s) to Grade 1 or baseline value, with the following exceptions:

- Subjects may resume treatment in the presence of Grade 2 fatigue.
- Subjects who have not experienced a Grade 3 drug-related skin AE may resume treatment in the presence of Grade 2 skin toxicity.
- Subjects with baseline Grade 1 AST/ALT or total bilirubin who require dose delays for reasons other than a 2-grade shift in AST/ALT or total bilirubin may resume treatment in the presence of Grade 2 AST/ALT or total bilirubin.
- Drug-related pulmonary toxicity, diarrhea, or colitis must have resolved to baseline before treatment is resumed.
- Subjects who received systemic corticosteroids for management of any drug-related toxicity must be off corticosteroids or have tapered down to an equivalent dose of prednisone ≤ 10 mg/day.
- Drug-related endocrinopathies adequately controlled with only physiologic hormone replacement may resume treatment.

During weeks 1-24, ipilimumab may not be resumed sooner than 6 weeks (-2/+3 days) after the prior dose. In general, it should be feasible to synchronize dosing of both nivolumab and ipilimumab drugs when resuming treatment. In order to facilitate this, the dosing days of nivolumab and ipilimumab may be adjusted within the permitted -2/+3day window, **as long as consecutive nivolumab doses are given at least 12 days apart.**

If an ipilimumab dose is delayed beyond 6 weeks from the prior ipilimumab dose, then subsequent ipilimumab doses should be rescheduled to maintain the 6 week interval between consecutive ipilimumab.

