5. TREATMENT

5.1 Systemic Therapy

5.1.1 Dosage and Administration

The treatment to be used in the run-in phase (initial 6 patients) of this trial is outlined in the table below. If ≤ 1 DLT is observed in the run-in phase, then the remaining 14 patients will be provided treatment per the following:

Drugs	Dose/Potency	Dose Frequency	Route of Administration	Regimen/Treatment Period
Weeks 1-24				
1. Nivolumab	3 mg/kg	Q2 weeks	IV infusion	Maximum of 12 doses
2. Ipilimumab	1mg/kg	Q6 weeks	IV infusion	Maximum of 4 doses
Weeks 25-52				
1. Nivolumab	480mg IV flat dose	Q4 weeks	IV infusion	Maximum of 8 doses

If 2 or more DLTs (defined in Section 5.1.2) are observed in the run-in phase, the following treatment will be used for the remaining 14 patients to be treated on the clinical trial protocol:

Drugs	Dose/Potency	Dose Frequency	Route of Administration	Regimen/Treatment Period
Weeks 1-24				
1. Nivolumab	3 mg/kg	Q4 weeks	IV infusion	Maximum of 6 doses
2. Ipilimumab	1mg/kg	Q8 weeks	IV infusion	Maximum of 3 doses
Weeks 25-52				
1. Nivolumab	480mg IV flat dose	Q6 weeks	IV infusion	Maximum of 4 doses

Patients who experience a DLT in the run-in phase, will have dose interruptions/reductions as outlined in Section 5.1.3.

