5.1.3 Dose Delays/Modifications

Toxicity will be graded using Common Terminology Criteria for Adverse Events (CTCAE version 5.0). The protocol will change to CTCAE version 6.0 if is published within the course of the trial.

Because the toxicities of both nivolumab and ipilimumab overlap, a patient meeting dose delay criteria within weeks 1- 24 will have ***both nivolumab and ipilimumab held until improvement of the adverse event to Grade 1 or baseline and retreatment criteria are met.***

Nivolumab may be delayed until the next planned ipilimumab if the next ipilimumab dose is scheduled within the next 12 days. This will permit periodic ipilimumab or ipilimumab-placebo dosing to be synchronized with nivolumab dosing.

Ipilimumab should be dosed at the specified interval regardless of any delays in intervening nivolumab doses. However, in order to maintain periodic synchronized dosing of ipilimumab and nivolumab, the dosing days of nivolumab and ipilimumab-may be adjusted within the permitted -2/+3 day window, as long as ***consecutive nivolumab doses are given at least 12 days apart.*** Ipilimumab may be delayed beyond the -2/+3 day window if needed to synchronize with the next nivolumab dose

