5.1.3.3 Criteria for permanent discontinuation of nivolumab and ipilimumab

An individual subject will not receive any further investigational product if any of the following occur in the subject in question:

- The subject or legal representative (such as a parent or legal guardian) withdraws consent.
- Confirmation of PD and investigator determination that the subject is no longer benefiting from treatment with nivolumab and ipilimumab
- Dosing delays lasting 12 weeks or more
- Inability to reduce corticosteroid to a dose of ≤ 10 mg of prednisone per day (or equivalent) **within 12 weeks** after last dose of study drug/study regimen
- Recurrence of a previously experienced Grade 3 treatment-related AE following resumption of dosing
- Adverse event that, in the opinion of the investigator or the sponsor, contraindicates further dosing
- Subject noncompliance that, in the opinion of the investigator or sponsor, warrants withdrawal; e.g., refusal to adhere to scheduled visits
- Subject is determined to have met one or more of the exclusion criteria for study participation at study entry and continuing investigational therapy might constitute a safety risk

- Intercurrent illness that prevents further administration of treatment
- Investigator's decision to withdraw the subject
- The subject has a confirmed positive serum pregnancy test
- Noncompliance with trial treatment or procedure requirements
- The subject is lost to follow-up
- Completed all doses of study drug
- Grade ≥ 3 infusion reaction

Subjects may withdraw consent at any time for any reason or be dropped from the trial at the discretion of the investigator should any untoward effect occur. In addition, a subject may be withdrawn by the investigator or the Sponsor if enrollment into the trial is inappropriate, the trial plan is violated, or for administrative and/or other safety reasons.

Subjects who are permanently discontinued from receiving investigational product will be followed for safety, including the collection of any protocol-specified blood specimens, unless consent is withdrawn or the subject is lost to follow-up or enrolled in another clinical study. All subjects will be followed for survival. Subjects who decline to return to the site for evaluations will be offered follow-up by phone every 3 months as an alternative.

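### Section 5.1.3.2 gives only a 6-week ipilimumab interval after a delay and makes no provision for the every-8-week modified regimen

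*Combined protocol and SAP*

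**What the plan says.** Section 5.1.1 has two dosing tables. The starting regimen gives ipilimumab 1 mg/kg every 6 weeks, at most 4 doses, in weeks 1-24. If 2 or more DLTs occur in the run-in, "the following treatment will be used for the remaining 14 patients to be treated on the clinical trial protocol": ipilimumab 1 mg/kg every 8 weeks, at most 3 doses, with nivolumab every 4 weeks, over the same 24 weeks.

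Section 5.1.3.2 sets the resumption rules for weeks 1-24 without distinguishing the regimens. It states two 6-week rules for ipilimumab:

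- A minimum: "ipilimumab may not be resumed sooner than 6 weeks" after the previous dose, with a -2/+3 day window.
- A rescheduling rule, triggered once a dose is more than 6 weeks after the one before it. The instruction in that case is that "subsequent ipilimumab doses should be rescheduled to maintain the 6 week interval between consecutive ipilimumab".

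Three provisions elsewhere bear on this. Section 5.1.3 says that "Ipilimumab should be dosed at the specified interval regardless of any delays in intervening nivolumab doses". It also says that a patient who meets the delay criteria in weeks 1-24 has "both nivolumab and ipilimumab held until improvement of the adverse event to Grade 1 or baseline", and that "Ipilimumab may be delayed beyond the -2/+3 day window if needed to synchronize with the next nivolumab dose". Section 5.1.3.3 ends treatment for "Dosing delays lasting 12 weeks or more". Footnote f of the Schedule of Assessments (Section 7) sends the reader to 5.1.1 for ipilimumab administration.

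**The concern.** The ipilimumab dose is 1 mg/kg in both tables, so the de-escalation consists entirely of wider spacing and the lower dose cap that goes with it. A resumption rule that names only 6 weeks brings back the starting regimen's spacing after a delay. The patients concerned are in the regimen adopted because of excess DLTs, and have just had a dose delayed, which under 5.1.3.1 would usually be for toxicity. At stake are the interval between two ipilimumab doses in those patients and consistent handling of delays. The primary analysis is not affected.

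**Working it through.** **Inputs.** Intervals, dose caps and the weeks 1-24 period are from 5.1.1. The 6-week rules and the -2 day window are from 5.1.3.2. The 12-week discontinuation limit is from 5.1.3.3.

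**The plan's own dose caps.** Counting from week 1 within weeks 1-24, every 6 weeks gives weeks 1, 7, 13, 19 = 4 doses, and every 8 weeks gives weeks 1, 9, 17 = 3 doses. Both stated maxima are reproduced.

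**Rescheduling rule on the modified regimen.** Let dose 2 be d weeks late, so it is given at week 9+d.

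- Literal 5.1.3.2: dose 3 at 9+d+6 = week 15+d.
- Assigned interval: dose 3 at 9+d+8 = week 17+d.
- Ratio of gaps: 6/8 = 0.75, so 25% shorter. Over that one gap the rate is 1/6 = 0.167 against 1/8 = 0.125 mg/kg per week, or +33%.
- Span from dose 1 to dose 3: 14+d weeks against 16+d (planned: 16).

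| d (weeks late) | Dose 2 | Dose 3, literal | Dose 3, assigned interval |
|---|---|---|---|
| 1 | week 10 | week 16 | week 18 |
| 2 | week 11 | week 17 | week 19 |
| 4 | week 13 | week 19 | week 21 |
| 8 | week 17 | week 23 | week 25 |
| 9 | week 18 | week 24 | week 26 |

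Dose 3 precedes its planned week 17 only if 15+d < 17, which among whole weeks means d = 1. If the 12-week limit is counted from the planned date, d runs from 1 to 11. Both rules place dose 3 by week 24 when 17+d ≤ 24 (d ≤ 7). Only the 6-week rule does so for d = 8 or 9 (15+d ≤ 24), and neither does for d = 10 or 11.

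**Fit of the trigger.** An on-time 8-weekly dose falls on day 56, already 56 − 42 = 14 days past the 6-week condition. On this regimen the condition cannot tell an on-time dose from a late one.

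**Minimum for resuming.** It is 6×7 = 42 days (40 with the window), against an assigned 8×7 = 56 (54). This only permits earlier dosing. Modified nivolumab visits are weeks 1, 5, 9, 13, 17, 21. The minimum therefore matters only when both drugs are held at week 5 or 13 and the hold clears before ipilimumab is due. A week-5 hold cleared by week 7 would permit ipilimumab at week 7 instead of week 9; a week-13 hold cleared by week 15 would permit week 15 instead of week 17.

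**How likely the modified regimen is.** The documents give no DLT rate. Assume independent per-patient rates of 10%, 20% and 30%, and count patients with a DLT. The 30% matches the plan's planning rate for grade 3 or higher acute drug-related toxicity, a related but different endpoint. The chance of 2 or more in 6 is 1 − (1−p)^6 − 6p(1−p)^5 = 11%, 34% and 58%. No delay rate is given either, so no count of affected patients can be offered.

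**The case against.** The strongest reply is that the rest of the protocol already points to 8 weeks.

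- *The specified interval.* Section 5.1.3 keeps ipilimumab on that interval despite nivolumab delays, and on the modified regimen it is 8 weeks. A hold at week 5 or 13 misses only a nivolumab dose, so this largely disposes of the minimum-interval scenario. It says nothing about rescheduling after ipilimumab's own delay, which is what 5.1.3.2 addresses.
- *The text presupposes a 6-weekly patient.* The trigger does not fit 8-weekly dosing, so the sentence is best read as describing the starting regimen. That is a reasonable inference, but it leaves the modified regimen with no rescheduling rule.
- *Synchronisation.* If nivolumab also restarts at week 9+d on a 4-week cycle, its next visits are 13+d and 17+d. A dose at 15+d falls 14 days after 13+d, outside the 12-day allowance for holding nivolumab back to match ipilimumab. Letting ipilimumab wait for nivolumab gives 17+d, exactly 8 weeks. The wait is optional, however. If nivolumab keeps its original calendar instead, both d = 1 and d = 2 lead to week 17, giving gaps of 17−10 = 7 and 17−11 = 6 weeks, so synchronising does not restore 8.
- *Negligible consequence.* One gap is affected, and dose 3 runs ahead of the original calendar only at d = 1, by one week. At d = 2 the three doses span the planned 16 weeks, so the +33% applies to a single gap and not to the course. The toxicity must also have resolved to the resumption criteria first. All of this stands, and it limits the point to a minor one.

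**Conclusion.** The concern holds. Six weeks is the only ipilimumab interval in 5.1.3.2, and nothing elsewhere requires 8 weeks after a delayed ipilimumab dose. Read literally, the rule shortens the dose 2 to dose 3 gap from 8 weeks to 6 on the modified regimen. The minimum-interval rule adds little, because 5.1.3 largely covers that case.

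The conclusion rests on a literal reading of 5.1.3.2, on the modified regimen being triggered, and on dose 2 being delayed. It could concern at most the 14 expansion patients. On-time doses, the 3-dose cap, endpoints, analyses and sample size are unchanged. It is worth correcting, but it does not threaten the trial's conclusions.

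**What to change.** In 5.1.3.2, replace the 6-week minimum with *the ipilimumab interval of the assigned regimen (6 weeks standard, 8 weeks modified; Section 5.1.1)*. Make the same substitution in both places where the rescheduling sentence names 6 weeks: the condition that triggers it and the interval to be kept.

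The cost is protocol wording only. There is one small downside: after a dose-2 delay of 8 or 9 weeks, dose 3 would fall at week 25 or 26, beyond the weeks 1-24 ipilimumab period, where the 6-week rule would have placed it at week 23 or 24. The amendment should say whether such a dose is given or omitted.

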5.1.3.3 Criteria for permanent discontinuation of nivolumab and ipilimumab

An individual subject will not receive any further investigational product if any of the following occur in the subject in question:

- The subject or legal representative (such as a parent or legal guardian) withdraws consent.
- Confirmation of PD and investigator determination that the subject is no longer benefiting from treatment with nivolumab and ipilimumab
- Dosing delays lasting 12 weeks or more
- Inability to reduce corticosteroid to a dose of ≤ 10 mg of prednisone per day (or equivalent) **within 12 weeks** after last dose of study drug/study regimen
- Recurrence of a previously experienced Grade 3 treatment-related AE following resumption of dosing
- Adverse event that, in the opinion of the investigator or the sponsor, contraindicates further dosing
- Subject noncompliance that, in the opinion of the investigator or sponsor, warrants withdrawal; e.g., refusal to adhere to scheduled visits
- Subject is determined to have met one or more of the exclusion criteria for study participation at study entry and continuing investigational therapy might constitute a safety risk

- Intercurrent illness that prevents further administration of treatment
- Investigator's decision to withdraw the subject
- The subject has a confirmed positive serum pregnancy test
- Noncompliance with trial treatment or procedure requirements
- The subject is lost to follow-up
- Completed all doses of study drug
- Grade ≥ 3 infusion reaction

Subjects may withdraw consent at any time for any reason or be dropped from the trial at the discretion of the investigator should any untoward effect occur. In addition, a subject may be withdrawn by the investigator or the Sponsor if enrollment into the trial is inappropriate, the trial plan is violated, or for administrative and/or other safety reasons.

Subjects who are permanently discontinued from receiving investigational product will be followed for safety, including the collection of any protocol-specified blood specimens, unless consent is withdrawn or the subject is lost to follow-up or enrolled in another clinical study. All subjects will be followed for survival. Subjects who decline to return to the site for evaluations will be offered follow-up by phone every 3 months as an alternative.

5.2 Radiation Therapy

All subjects will be immobilized in a custom designed device in the appropriate position to isolate the index lesion. Radiotherapy treatment planning CT scans (with contrast, unless contraindicated) will be required to define the gross target volume (GTV) and planning target volume (PTV). PET-CT and/or MRI imaging are preferred to delineate volumes as accurately as possible. The treatment planning CT scan should be acquired with the subject in the same position and immobilization device, as for the treatment. Treatment planning will be done using a 3D based CT treatment planning system. All tissues to be irradiated must be included in the CT scan. Planning CT scan will be done at 1.25 mm intervals from encompassing the region of interest with sufficient margin for treatment planning.

5.2.1 Stereotactic Targeting and Treatment

SBRT has now been formally defined and described in a published guideline from the American College of Radiology and American Society for Therapeutic Radiology and Oncology (Potters, 2004). This protocol will respect that guideline. The term stereotactic, for the purposes of this protocol, implies the targeting, planning, and directing of therapy using beams of radiation along any trajectory in 3-D space toward a target of known 3-D coordinates. The coordinate system is defined by reliable “fiducial” markers. This differs from conventional radiation therapy, in which therapy is directed toward less-than-reliable skin marks or bony landmarks that are indirectly referenced to the tumor (surrogates). This protocol will require treatments to be conducted with the use of a fixed 3-D coordinate system defined by fiducials. The coordinate system defined by the fiducials should be directly related to the radiation-producing device in a reproducible and secure fashion. Capability should exist to define the position of targets within the patient according to this same 3-D coordinate system. As such, the patient is set up for each treatment with the intention of directing the radiation toward a target according to the known 3-D coordinates as determined in the process of treatment planning. The nature of the fiducials themselves may include radiopaque markers or rods placed at known locations in a frame or fixed structure adjacent to the patient as well as use of the tumor itself as a fiducial (e.g., acquiring tomographic views of the tumor simultaneously with the treatment). Metallic “seeds” placed within the tumor will be allowed to constitute a fiducial so long as the methods are validated and a plan is in place to identify seed migration (e.g., redundant seeds placed).

5.2.2 Target Contouring

Gross Tumor Volume (GTV) is defined as all known gross disease encompassing the selected index lesion. The GTV will consist of the index lesion as visualized on CT +/- PET/CT, and/or MRI. Image fusion is encouraged when using multiple modalities to define the GTV.

Clinical Target Volume (CTV) will be the same as GTV for most cases. In case of uncertainty, GTV could be expanded to CTV by 2-3mm per clinician discretion.

Internal Gross Tumor Volume (IGTV) is defined for mobile index lesions at the discretion of the treating physician. For mobile index lesions, a 4-D CT scan will be acquired in order to account for the motion of the lesion during treatment. The IGTV will be defined as the union of the visualized index lesion on all gated CT data sets.

Planning Target Volume (PTV) will be defined as per convention for photon beam radiotherapy. A 3-dimensional margin of 3-5mm will be created on the CTV or IGTV (if available) to allow for daily set-up variance. For Proton beam radiotherapy, an additional range uncertainty is added during planning.

Organ at Risk volume (OAR) is contoured as visualized on the planning CT or MR scan.

Planning organ at Risk Volume (PRV) is the OAR expanded for setup uncertainty or organ motion. The physician will contour the OAR. The dosimetrist will create the PRV by expanding the OAR by 1-3 mm, depending on the situation.

Pertinent Organs at Risk (OARs) in the index region are contoured as applicable:

Spinal cord, Brain stem, Brachial plexus (roots & trunks)
Optic pathways – optic nerves, optic chiasm, Retina, Cornea
Carotid artery (Internal & common),
Cochlea & vestibular apparatus
Skin (3-5 mm of body outline)
Larynx (infrahyoid supraglottis to bottom of cricoid. Only include the endolarynx within the cartilaginous framework)
Other uninvolved mucosal structures e.g.: oral cavity & pharynx
Facial Bones: Mandible, Maxilla, temporal bone that pertain to index region
Esophagus
Heart and Pericardium
Lungs
Ribs
Trachea and Large/Central Bronchi
Bronchii – smaller airways

5.2.3 Treatment planning, dose fractionation and specification

Computer based planning & QA will be performed using our standard institutional SBRT guidelines, including corrections for tissue heterogeneity, and robustness analysis (for Proton therapy). Treatment planning may be done with IMRT, VMAT, Proton beam RT (Pencil beam RT or Uniform scanning).

The dose prescription will be as follows: 24 Gy given in 3 fractions to PTV (80-95% IDL) delivered at 8 Gy per fraction every other day.

Dose rate: For the purpose of this study, dose rate utilized will be that which is commissioned by the manufacturer and the medical physics group for external beam radiotherapy delivery by the treating institution. There will be no special dose rate modifications required for this study.

The following PRV dose constraints will be used: (adopted from Timmerman RD. An overview of hypofractionation. Seminars of Radiation Oncology 2008 Oct;18(4):215-222).

Spinal cord max 21Gy, 18Gy (< 0.35cc), 12 Gy (<1cc)

Brain stem max 23 Gy, 18 Gy (< 0.5cc)

Optic chiasm max 15 Gy, 12 Gy (< 0.2cc) (for bilateral blindness risk)

Ipsilateral Optic nerve max 18 Gy, 15 Gy (< 0.2cc)

Contralateral optic nerve max 12 Gy, 10 Gy (< 0.5cc)

Carotid artery max 15 Gy, (V12 Gy to < 30% of carotid volume)

Brachial plexus max 24 Gy, 20 Gy (< 3cc)

Esophagus* max 24 Gy, 17 Gy (< 5cc)

Heart/Pericardium max 24 Gy, 20 Gy (< 15cc)

Trachea* max 24 Gy, 15 Gy (< 4cc)

Bronchus max 23 Gy, 18 Gy (< 1cc)

Ribs max 24 Gy, 20 Gy (< 5cc)

Skin 24 Gy (< 10cc), 20 Gy (<10cc)

Lung (Right & Left) – Volume to spare > 1000cc to </= 12 Gy and
> 1500 cc to </= 11.5 Gy, V15 Gy < 35%

Liver – spare >700cc to </=19 Gy

Stomach – max 22 Gy, 16 Gy to < 10cc

Rest of OARS = ALARA

* avoid circumferential radiation

Three-dimensional coplanar or non-coplanar beam arrangements will be custom designed for each case to deliver highly conformal prescription dose distributions. Non-opposing, noncoplanar beams are preferable. Typically, ≥ 10 beams of radiation will be used with roughly equal weighting for photon planning. Generally, more beams are used for larger lesion sizes. When static beams are used, a minimum of 7 non-opposing beams should be used. For arc rotation techniques, a minimum of 340 degrees (cumulative for all beams) should be utilized. For arc rotation techniques, a minimum of 340 degrees (cumulative for all beams) should be utilized.

Proton beam planning is performed with 2-4 beams. In order to obtain acceptable coverage, field aperture size and shape should correspond nearly identically to the projection of the PTV along a beam's eye view (i.e., no additional "margin" for dose buildup at the edges of the blocks or MLC jaws beyond the PTV). The only exception should be when observing the minimum field dimension of 3.5 cm when treating small lesions (see above). As such, prescription lines covering the PTV will typically be the 60-90% line (where the maximum dose is 100%); however, higher isodoses (hotspots) must be manipulated to occur within the target and not in adjacent normal tissue. The treatment isocenter or setup point in stereotactic coordinates will be determined from system fiducials (and can be adjusted pretreatment depending on the results from localization imaging studies) and translated to the treatment record.

Dose specifications

Successful treatment planning will require accomplishment of all of the following criteria:

1. Maximum dose: The treatment plan should be created such that 100% corresponds to the maximum dose delivered to the patient. This point must exist within the PTV.
2. Prescription isodose: The prescription isodose surface must be $\geq 60\%$ and $< 90\%$ of the maximum dose.
3. Prescription Isodose Surface Coverage: The prescription isodose surface will be chosen such that 95% of the target volume (PTV) is conformally covered by the prescription isodose surface (PTV V95%RX = 100%) and 99% of the target volume (PTV) receives a minimum of 90% of the prescription dose (PTV V90%RX $> 99\%$).
4. High Dose Spillage: The cumulative volume of all tissue outside the PTV receiving a dose $> 105\%$ of prescription dose should be no more than 15% of the PTV volume. Conformality of PTV coverage will be judged such that the ratio of the volume of the prescription isodose meeting criteria 1 through 4 to the volume of the PTV is ideally $<$

1.2 (see table below). These criteria will not be required to be met in treating very small tumors (< 2.5 cm axial GTV dimension or < 1.5 cm craniocaudal GTV dimension) in which the required minimum field size of 3.5 cm results in the inability to meet a conformality ratio of 1.2. The “None” and “Minor” entries in this table define the Per Protocol, Variation Acceptable and Deviation Unacceptable Compliance Criteria.

5. Intermediate Dose Spillage: The falloff gradient beyond the PTV extending into normal tissue structures must be rapid in all directions and meet the following criteria:

- Location: The maximum total dose over all fractions in Gray (Gy) to any point 2 cm or greater away from the PTV in any direction must be no greater than D_{2cm} where D_{2cm} is given by the table below.
- Volume: The ratio of the volume of the 34 or 12 Gy isodose volume to the volume of the PTV must be no greater than R_{50%} where R_{50%} is given by the table below (adapted from RTOG 0915). This table is used for all prescription requirements irrespective of calculation algorithm and total treatment dose.

Table 1: Conformality of Prescribed Dose for Calculations Based on Deposition of Photon Beam Energy in Heterogeneous Tissue

PTV Volume (cc)	Ratio of Prescription Isodose Volume to the PTV Volume		Ratio of 50% Prescription Isodose Volume to the PTV Volume, R _{50%}		Maximum Dose (in % of dose prescribed) @ 2 cm from PTV in Any Direction, D _{2cm} (Gy)	
	Deviation		Deviation		Deviation	
	None	Minor	None	Minor	None	Minor
1.8	<1.2	<1.5	<5.9	<7.5	<50.0	<57.0
3.8	<1.2	<1.5	<5.5	<6.5	<50.0	<57.0
7.4	<1.2	<1.5	<5.1	<6.0	<50.0	<58.0
13.2	<1.2	<1.5	<4.7	<5.8	<50.0	<58.0
22.0	<1.2	<1.5	<4.5	<5.5	<54.0	<63.0
34.0	<1.2	<1.5	<4.3	<5.3	<58.0	<68.0
50.0	<1.2	<1.5	<4.0	<5.0	<62.0	<77.0
70.0	<1.2	<1.5	<3.5	<4.8	<66.0	<86.0
95.0	<1.2	<1.5	<3.3	<4.4	<70.0	<89.0
126.0	<1.2	<1.5	<3.1	<4.0	<73.0	>91.0
163.0	<1.2	<1.5	<2.9	<3.7	<77.0	>94.0

Image guided RT (IGRT) is required with physician review per institutional QA requirements before each treatment is delivered. Cone beam CT will be matched to target volume to be treated and bony anatomy or other defined fixed fiducials. If CBCT is unavailable, orthogonal pair KV imaging matched to bony anatomy closest to PTV is acceptable.

